#### 5.4 Drop-out Criteria

All subjects who signed informed consent and were screened for inclusion in the trial, regardless of when and for any reason, were drop-out cases, including:

(1) The subject requested to withdraw from the clinical trial.

(2) Adverse events or serious adverse events (SAE) occurred, which

prevented the subject from continuing to participate in the trial.

(3) The subjects had poor compliance or lost follow-up, and failed to follow up according to the trial protocol.

(4) The investigator considers it medically necessary to suspend the subject test.

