#### 4.4 After Surgery

(1) The physician should provide the patient with a detailed description of the limitations of the product. Patients should be warned that complications such as bending, loosening or breaking of the implant may be caused by excessive weight bearing, excessive muscle activity or sudden impact on the surgical site. Patients should be told how to limit and control physical activity and advised to avoid strenuous exercise and excessive weight bearing.

(2) During the healing stage of the fracture, the physician should advise the patient not to smoke or drink too much alcohol.

(3) It is very important to confirm whether bone healing occurs after the

operation by X-ray. Bone non-union or delayed healing during the treatment stage will cause the implant to be subjected to repeated stress for a long time, which may fatigue the product and eventually bend, loosen or fracture. Therefore, if non-healing occurs or if the implant is loose, bent or broken, the implant should be adjusted or removed when serious damage is imminent.

(4) Any removed implants should be properly disposed of to ensure that the product will not be used in other surgeries.

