#### 5.7 Expected Duration of Participation for Each Subject

According to the Guiding Principles for the Technical Review of Product Registration of Metal Intramedullary Nail System and the Guiding Principles for the Technical Review of Registration of calcium phosphorus/Silicon bone filling Materials, the clinical healing time of periarticular fractures of limbs is about 24 weeks, and the tissue reaction of degradable implants should be followed up until the tissue reaction of the products reaches a stable state after implantation. According to the literature search of controlled products, absorbable screws can reach a stable state about 12 months after implantation. In order to fully observe the clinical safety of the product, the participation time of each subject will be 18 months after surgery, so the expected participation time of each subject is about 18 months.

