#### **B.** Serious adverse event reporting process

If a serious adverse event occurs in a clinical trial, the investigator shall immediately take appropriate treatment measures for the subject; meanwhile, the investigator shall report the serious adverse event to the sponsor, the management department of the medical device clinical trial institution, and the ethics committee within 24 hours after learning about it; Serious adverse events were followed up in accordance with the provisions of the clinical trial protocol, and serious adverse event follow-up reports were submitted.

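### Section 5.4 groups adverse-event, non-compliance and investigator-decided exits with withdrawal of consent, and neither document requires any further assessment, so obtainable week-24 healing outcomes can be lost

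*Protocol*

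**What the plan says.** Protocol 5.4 treats subjects who leave, "regardless of when and for any reason, were drop-out cases", as one class with four listed reasons:

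1. The subject asks to withdraw.
2. An adverse event or SAE "prevented the subject from continuing to participate in the trial".
3. Non-compliance or loss of contact, combined with missed protocol visits.
4. A decision by the site, worded as "The investigator considers it medically necessary to suspend the subject test".

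Neither document says what is collected after any of these. Protocol 5.7 plans that "the participation time of each subject will be 18 months after surgery". Its stated reasons include that "the tissue reaction of degradable implants should be followed up until the tissue reaction of the products reaches a stable state after implantation". Protocol section 2 (Masking) says investigators cannot be blinded.

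Three provisions keep part of the safety information:

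- The SAE reporting section states that "Serious adverse events were followed up in accordance with the provisions of the clinical trial protocol" and asks for follow-up reports.
- SAP section 7C asks that discontinuations due to adverse events, and SAEs, be specifically noted.
- SAP section 9 puts every subject who used the device in the safety set.

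SAP section 4 expects drop-out of at most 15%. SAP section 7 announces in its title a treatment of dropouts and withdrawals, but its text only lists the dropped cases.

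**The concern.** Treatment here is one operation. Suspending a drug subject can mean stopping the drug while visits continue. After implantation there is nothing left to stop except the assessments, so a site would naturally read drop-out, or suspension of the subject's test, as the end of data collection. The fracture and usually the screw are still there to be examined. Protocol 4.4 does foresee cases in which "the implant should be adjusted or removed when serious damage is imminent", so the screw does not always remain.

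Two of the four reasons, a participation-preventing adverse event and a medical decision by the investigator, could plausibly be linked to failed fixation, and an investigator who knows the arm makes the second decision. If such subjects leave without a week-24 examination and X-ray, the primary outcome is missing where it may be most informative, and no analysis rule can recover it. Later non-serious adverse events, laboratory results and imaging can be lost in the same way.

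**Working it through.** **Inputs.** Control healing 95.5%, test healing comparable, margin -10 points, two-sided alpha 0.05, power 0.80 (SAP section 3); drop-out at most 15% (SAP section 4); success if the lower 95% limit exceeds -10% (SAP section 5); 80 per arm (Protocol 5.9).

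**The plan's own figure.** With equal rates, n = (1.960 + 0.842)² × 2 × 0.955 × 0.045 / 0.10² = 67.46, rounded up to 68 per arm, as stated. Then 68 / (1 - 0.15) = 80 per arm, 160 in total. The 160 therefore allows for 0.15 × 160 = 24 subjects (12 per arm if balanced) without a primary outcome.

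**Model for the effect of the loss.** Assume a completers-only analysis and true healing exactly at the margin. The test completer rate c follows from the whole-arm rate and the assumed drop-out healing rate. The false-pass chance is the exact sum over two binomials, 68 completers per arm, of all results whose lower limit exceeds -10%. The SAP does not name an interval method, so Wald and Newcombe are both shown. In cases A to C true healing is 85.5% (test) v 95.5% (control), and control drop-outs heal like control completers.

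- A. Uninformative drop-out: c = 0.855.
- B. All test drop-outs heal at 50%: c = (0.855 - 0.15 × 0.50) / 0.85 = 0.918. The completer gap is -3.7 points although the true gap is -10.
- C. One third of test drop-outs heal at 50%, the rest like completers: c = (0.855 - 0.05 × 0.50) / 0.95 = 0.874.
- D. Drop-outs in both arms heal at 50%, control completers at 95.5%. Control overall = 0.85 × 0.955 + 0.15 × 0.50 = 0.887; test overall, 10 points lower, = 0.787; c = (0.787 - 0.075) / 0.85 = 0.837. The completer gap is -11.8 points, wider than the truth.

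| Case | False pass, Wald | False pass, Newcombe |
|---|---|---|
| A. Uninformative | 4.0% | 2.2% |
| B. All test drop-outs at 50% | 38.4% | 25.4% |
| C. One third of test drop-outs at 50% | 8.7% | 5.0% |
| D. Drop-outs in both arms at 50% | 1.8% | 1.0% |

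With case B's structure, drop-out healing of 30% gives 79.8% (Wald) or 64.2% (Newcombe), and 70% gives 12.2% or 7.1%.

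**What retention would recover.** If half the drop-outs are still assessed at week 24, n = 80 - 6 = 74 per arm. In case B, c = (0.855 - 0.075 × 0.50) / 0.925 = 0.884, and false pass falls from 38.4% to 13.4% (Wald) or from 25.4% to 7.7% (Newcombe). With both arms at 95.5%, exact power rises from 82.0% to 85.2% (Wald) or from 66.8% to 72.6% (Newcombe). This gain needs no assumption about informative drop-out.

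**The case against.** The strongest reply is that section 5.4 only labels subjects. A reader might infer that it forbids further visits, or that any adverse event makes a drop-out. The documents support neither: they are silent on visits after drop-out, and reason 2 covers only an event that prevents participation. Reason 3 mainly describes people who have already stopped attending, so the wording does not cause that loss. No rule makes a subject seen outside the week-24 window a drop-out. All of this stands. The defect is an omission, not an instruction to stop.

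A reader might also see a contradiction with Protocol 5.7 or with the SAE section. There is none. Section 5.7 explains the planned duration, and the SAE section requires follow-up without excepting drop-outs. Nor are safety data wholly lost, given that requirement and SAP sections 7C and 9. What is exposed is later non-serious events, laboratory tests and imaging.

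Finally, it is tempting to say that the loss favours a non-inferiority claim. That needs test drop-outs to do worse, relative to completers, than control drop-outs. If failed fixation drives drop-out in both arms alike, case D applies and false passes become rarer. Case B also uses the 15% ceiling, makes every test drop-out informative and assumes a completers-only analysis, which the SAP does not specify. If drop-outs counted as not healed, these figures would not apply. The objection therefore removes the claim of direction and the use of 38% as an expected value. It does not answer the absence of any required assessment.

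**Conclusion.** The point holds as an avoidable gap in data collection. Three reasons that do not oblige data collection to stop are classed with withdrawal of consent, and no further assessment of those subjects is required. Up to 24 of 160 week-24 outcomes are at risk, some of which could be obtained.

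The possible effect on the primary result ranges from a false-pass chance of 1.8% or 1.0% (both arms at 50%), through 8.7% or 5.0%, to 38% or 25% (all test drop-outs at 50%, control drop-outs unaffected), Wald and Newcombe respectively. All of these rest on assumed drop-out healing rates, 15% drop-out in each arm and a completers-only analysis; the documents give no drop-out outcomes. Distortion requires drop-out that is informative and differs by arm. Its direction cannot be stated in advance, but the loss of precision can. How a missing week-24 outcome is handled in the analysis is a separate question.

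**What to change.** Amend Protocol 5.4 to separate (a) withdrawal of consent to follow-up from (b) every other reason. State that subjects under (b) stay on the existing scheduled assessments where they can be reached. The minimum is the week-24 clinical examination and X-ray, plus adverse event and device status to week 72. If a window is missed, the assessment is still made and its actual date recorded. Record the reason for and date of every drop-out.

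The cost is a wording amendment plus site effort. The visits, X-rays and recordings already exist in the schedule (Trial Procedure 2.4 to 2.8) and are planned for all 160 subjects. The effort is recalling up to about 24 subjects, some of whom, especially under reason 3, may be unreachable. The sample size does not change.

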#### 5.5 Criteria and Procedures for Trial Termination

(1) Major errors or deviations in the clinical trial protocol are found in the trial, making it difficult to evaluate the safety and effectiveness of the test products.

(2) The sponsor (e.g., for financial reasons, administrative reasons, etc.) requested termination of the trial.

(3) The administrative authority revokes the trial.

In case of the above situation, the sponsor shall promptly notify the researchers, the medical device clinical trial institutions and the ethics Committee. For subjects who have been treated with experimental devices, the sponsor shall fulfill its responsibilities to the subjects during the trial in accordance with the contents of the signed informed consent.

#### 5.6 Group Entry Time

After signing the informed consent form, meeting the inclusion criteria and not meeting the exclusion criteria, the time when the subject underwent randomization was the enrollment time.

#### 5.7 Expected Duration of Participation for Each Subject

According to the Guiding Principles for the Technical Review of Product Registration of Metal Intramedullary Nail System and the Guiding Principles for the Technical Review of Registration of calcium phosphorus/Silicon bone filling Materials, the clinical healing time of periarticular fractures of limbs is about 24 weeks, and the tissue reaction of degradable implants should be followed up until the tissue reaction of the products reaches a stable state after implantation. According to the literature search of controlled products, absorbable screws can reach a stable state about 12 months after implantation. In order to fully observe the clinical safety of the product, the participation time of each subject will be 18 months after surgery, so the expected participation time of each subject is about 18 months.

# 5.8 The Expected Overall Duration of Clinical Trials and the Reasons for Determination

The overall duration of the clinical trial includes the ethical approval of all clinical trial institutions and the modification of opinions after the ethical review, the signing time of the clinical trial agreement, the filing time of the clinical trial, the start of the clinical trial, the enrollment time and the examination time of the subjects, the collection time of clinical trial data, the statistics time and the writing time of the summary report. Combined with the number of cases to be completed in this study, the number of cases in each research center and other factors, the final estimated time to complete this clinical trial is about 18-22 months.

#### 5.9 Number of Subjects Required for Clinical Trials

A total of 160 subjects were planned to be included, and 80 subjects in the experimental group and the control group respectively. The trials were conducted in 6 medical institutions qualified to carry out clinical trials of medical devices, and were distributed according to the capacity of the medical institutions to bear the number of subjects and the principles of statistics.

#### **6** Effectiveness Evaluation

#### **6.1 Validity Parameter**

6.1.1 Primary Outcome: Clinical fracture healing rate at 24 weeks after surgery

6.1.2 Secondary Index:

(1) Clinical fracture healing rate at 12, 48 and 72 weeks after surgery

(2) Pain score

- (3) Joint function score
- (4) Device performance index

#### **6.2 Description of Validity Parameters**

6.2.1 Main Efficacy Evaluation Index: Clinical fracture healing rate at 24 weeks after surgery

Evaluation Criteria:

(1) No local tenderness and longitudinal tapping pain, no local

abnormal activity.

(2) The X-ray shows a continuous callus or trabecular bone across the fracture line, which has been blurred.

Note: If both of the above two points are satisfied, it is considered healed; otherwise, it is not healed.

Healing rate = (Healing cases/Total cases)  $\times$  100%

Evaluation Time: 24 weeks  $\pm$  4 week

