#### 5.3 Remove Criteria

(1) No devices were used after enrollment.

(2) Violation of inclusion or exclusion criteria.

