#### (2) Device Defect

Device defect refers to the unreasonable risks that may endanger human health and life safety under normal use of medical devices in the course of clinical trials, such as label errors, quality problems, failures, etc. In the course of this clinical trial, if the use of devices fails due to device defects, the investigator shall conduct routine treatment according to clinical needs. The investigator should document all discovered device defects that occur during clinical trials.

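### Read literally, the week-24 healing rule counts a fracture that united after surgical re-intervention on the study screw as a success for that screw

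*Protocol*

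**What the plan says.** Protocol 6.2.1 sets two conditions for healing at 24 weeks: absence of the listed clinical signs, and bridging callus or trabeculae on X-ray. It then closes the rule: "If both of the above two points are satisfied, it is considered healed; otherwise, it is not healed". The state of the assigned screw is not a condition. The rate is "Healing rate = (Healing cases/Total cases"), with the denominator undefined.

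The protocol expects that some screws may fail. Section 4.4 says that "if the implant is loose, bent or broken, the implant should be adjusted or removed when serious damage is imminent". The Device Defect section says that "if the use of devices fails due to device defects, the investigator shall conduct routine treatment according to clinical needs". Neither says what happens to the subject's week-24 result.

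Other text might take such a subject out of the count. Protocol 5.3 removes subjects where "No devices were used after enrollment". Protocol 5.4 makes a drop-out of a subject with an adverse event that "prevented the subject from continuing to participate in the trial", or where "The investigator considers it medically necessary to suspend the subject test". SAP 9 limits the per-protocol set (PPS) to compliant subjects. None of these provisions mentions screw failure, and none makes the subject a treatment failure.

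Under SAP 5 the trial succeeds if the lower 95% limit for test minus control lies above -10%.

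**The concern.** The trial asks whether the test screw fixes the fracture as well as the control screw. If a screw loosens, is taken out, and the bone then unites under other fixation, the union says little about that screw. The written rule still credits it.

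Crediting such subjects pulls the two arms together. If the test screw fails more often, the rule hides part of its deficit, which favours non-inferiority. If the control screw fails more often, the rule works against the test screw. Either way, the one comparison that decides the trial is less able to show a difference in fixation. Investigators are not blinded (Protocol 2, Masking), so how these subjects are counted should be settled before results are seen.

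**Working it through.** **Inputs.** Assumed healing 95.5% in both arms, margin 10 points, two-sided alpha 0.05 and power 80% (SAP 3A); drop-out at most 15% (SAP 4); 80 subjects per arm (Protocol 5.9). The documents give no screw-failure rate, so all counts and failure fractions below are assumptions. The SAP names no interval method; Wald limits are shown, with Newcombe limits where they add something.

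**The plan's own figure.** n = (1.960 + 0.842)² × 2 × 0.955 × 0.045 / 0.10² = 67.46, rounded up to 68 per arm. Then 68/0.85 = 80 per arm. Both stated figures reproduce.

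**Effect of crediting.** One subject moves an arm's rate by 1/80 = 1.25 points, one-eighth of the margin. The Wald lower limit is d - 1.96 × √[pT(1-pT)/80 + pC(1-pC)/80]. Start from 76/80 in each arm as literally scored, and recode test subjects who united after re-intervention as not healed:

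| Test | Control | Wald lower limit | Newcombe lower limit |
|---|---|---|---|
| 76/80 | 76/80 | -6.75% (pass) | -7.78% (pass) |
| 75/80 | 76/80 | -8.39% (pass) | -9.40% (pass) |
| 74/80 | 76/80 | -9.99% (pass) | -10.98% (fail) |
| 73/80 | 76/80 | -11.57% (fail) | -12.52% (fail) |

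For the row with two recoded: -0.025 - 1.96 × √(0.925×0.075/80 + 0.95×0.05/80) = -0.025 - 0.0749 = -0.0999.

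The opposite case exists too. 72/80 against 76/80 gives -13.13% (fail). Recoding four control subjects gives 72/80 against 72/80 and -9.30% (pass).

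**Power cost of scoring re-intervention as not healed.** Let a share f of each arm become automatic failures, independent of healing, so each rate is 0.955 × (1 - f). Power is by exact binomial enumeration of the Wald rule at 80 per arm:

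| f | Rate | Power, no other loss |
|---|---|---|
| 0% | 95.5% | 85% |
| 1% | 94.5% | 80% |
| 2% | 93.6% | 75% |
| 3% | 92.6% | 70% |
| 5% | 90.7% | 61% |

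With f = 2% and a further 10% or 15% lost and counted as not healed, the rates are 0.955 × 0.98 × 0.90 = 84.2% and 0.955 × 0.98 × 0.85 = 79.6%. Power is 41% and 35%. Loss of 15% by week 24 is the worst case, since the ceiling covers the whole trial.

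**Related gap: the denominator.** With illustrative completers of 72/76 against 73/76 the lower limit is -7.98% (pass). The same healed subjects over 80 per arm give -10.28% (fail). In a simulation with true healing 95.5% in both arms and equal loss of 5%, 10% or 15%, moving from completers to all randomised with missing counted as not healed turns a pass into a fail in about 26%, 39% or 46% of trials. It turns a fail into a pass in about 2%.

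**The case against.** The best defence is that counting union whatever happened to the screw is a legitimate question, close to intention to treat. That stands as a reason to report it, and the fix keeps it as a sensitivity analysis. It does not show that the sponsor chose it, because nothing in the documents discusses the case. For a device whose function is fixation, it is the less informative of the two counts.

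A reader might infer that the plan definitely credits failed screws. It does not go that far. The inference rests on the literal rule plus silence elsewhere, and the same subject could become a drop-out, leave the PPS or, if no device was used, be removed. The documents speak of adjustment, removal and routine treatment; exchange for another screw is only an example of what might follow.

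It is also fair that no failure rate is given. Protocol 5.7 puts healing at about 24 weeks, so mainly early failures could be re-treated and still unite in time.

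A reader might further infer that the open denominator is equally likely to produce a false success or a false failure. The figures do not support this: with equal loss the likely change is from pass to fail, and fail to pass mainly needs more loss in the control arm. Whether the full analysis set (FAS) or the PPS should be primary in a non-inferiority trial is itself a trade-off.

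**Conclusion.** The point holds as a gap in the scoring rule that should be fixed. As written, union after re-intervention on the study screw counts as a success for the assigned arm if the subject stays in follow-up, and no text makes that subject a failure. The likely effect is small. The counts above show that two or three test subjects can be enough to change the verdict, depending on the interval method; they do not show how likely that is.

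The undefined denominator, primary set, missing-data rule and interval method are real but secondary here. The heading of SAP 7 announces treatment of missing data and dropouts, but the section only lists dropped cases. The step from 68 to 80 implies that drop-outs leave the denominator, while the closing words of the healing rule can be read as keeping them as not healed. These gaps need an answer from the sponsor, but they do not make the point more than a should-fix.

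**What to change.** In Protocol 6.2.1 and SAP 7B, for counting only:

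1. Score as not healed any subject with a documented unplanned surgical procedure on the study screw or its fixation before the week-24 assessment: removal, adjustment, exchange or added surgical fixation. Include failure of the screw at the first operation that led to other fixation.
2. Apply this identically in both arms and whatever reason is recorded, so that it does not rest on a judgement by unblinded investigators. Exempt only auxiliary fixation planned before surgery, with one definition for both arms. Protocol 4.6 mentions auxiliary fixation only for the control device, so an exemption taken from that text would be uneven.
3. Keep these subjects in the denominator of their assigned arm.
4. Report healing regardless of re-intervention as a sensitivity analysis.
5. Before results are seen, define the denominator, the primary set (including how the Protocol 5.3 removals, among them "Violation of inclusion or exclusion criteria", are handled), the missing-data rule and the interval method. Report both FAS and PPS.

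The cost is document wording and one eCRF item for re-operation at the fracture site (date and type). Part of this is already captured through adverse events, serious adverse event reports and device-defect records. The other cost is lower healing rates and lower power, as tabulated, so power should be restated under the chosen rule over a range of loss by week 24; the sample may have to grow. No change to clinical management is proposed.
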